*** Identify the subgroups and provide a justification:**

Children are excluded. The physical activity requirements of 150 minutes of physical activity pertain only to adults. The intervention is designed for adults- materials specific to children would have to be designed for children.

8. Describe the power analysis used and cite your method of statistical analysis.

If a power analysis is not possible, thoroughly justify the sample size required for the study, including appropriate literature citation (alternatively provide page reference in attached protocol):

For our Aim 1a primary outcomes, we hypothesize that participants randomized to ActiveGOALSV2 + PAT will have significantly larger (a) increases in step counts/day and % meeting moderate-vigorous physical activity goal of 150 minutes/week (to 12 months) compared to the active PAT control group. Descriptive analyses and graphic displays will be used to identify outliers, missing data, and pattern of attrition. To ensure rigor, the primary analytic strategy will be a linear or generalized mixed-effect models approach in which treatment group, time, and time by group interaction are treated as fixed effects, and subject is treated as a random effect to account for individual subject variability (two sided hypothesis test; .05 level). Mixed models are applicable to longitudinal datasets that contain missing observations, (assuming data is missing at random). Regression modeling will be conducted to adjust for important covariates. We will perform similar analyses to examine changes in secondary outcomes. Descriptive statistics on patient experience, beliefs/attitudes related to maintenance of physical activity changes, and program cost will also be reported.

Power and sample size: For a 2 sided test with alpha level set at .05, and assuming 20% attrition at 12 months, we plan to recruit 54 participants to identify clinically relevant mean difference between randomized groups at 12-months of 2000 steps/day (with a power of .80), and 35% meeting MVPA goal (with a power of .80), given reference mean (sd) values were calculated from baseline waist worn accelerometer data from the current K12 of: 5250 (2200) steps/ day and we assume 5% meeting goal at baseline in the control group.

For Aim 1b, descriptive statistics will be used to describe the total eligible population, those referred, and those referred who participated in the study; in order to determine program reach. Exploratory Analysis of Important Pre-Existing Factors: Factor analysis will be used to identify importance of factors related to physical activity levels/ activity goal achievement over the 12 month follow-up (Mplus) from participant EHR data collected prior to intervention start. Factor structures of how individual factors contribute to activity outcomes will be explored at each time point. The best factor structure will be determined with Eigenvalues and fit indices (RMSEA, CFI, and TLI). Factor structures at the 2 time points will be compared at three levels to establish measurement invariance: 1) Configural equivalence, number of factors/ pattern of factor-indicator relationships are identical over time; 2) Metric equivalence, factor loadings are equal over time; and 3) Scalar equivalence, means and values are equivalent over time. Finally, we will use descriptive statistics to report presence/absence of data on physical activity levels, cardiometabolic, and patient-centered outcomes in the EHR. We will apply the same regression approaches utilized in Aim 1a to determine differences between randomized groups for EHR reported outcomes.

Research Activities

- 1. * Provide a detailed description of all research activities (including screening and follow-up procedures) that will be performed for the purpose of this research study. This description of activities should be complete and of sufficient detail to permit an assessment of associated risks.**

Development: Patient-partners will be recruited in the first 2 months of the study. They will be engaged by working with the PaTH Network's stakeholder engagement infrastructure and will participate in the monthly meetings held by the intervention team. Feedback received on intervention design and delivery, as well as, the need for any addition patient-centered outcomes, will be incorporated into the study design.

We will work with the UPITT Community Research Advisory Board (CRAB) during months 1-4 to develop recruitment materials. Modification of existing ActiveGOALS materials will take place in months 1-8 (including updated coaching materials). This will also include full-integration of a PAT device. In months 8-12 we will develop the 9 monthly maintenance sessions. Staff hiring and training will take place in months 8-12; this will include at least 1 student worker to help with recruitment and retention and 1 graduate student coach with a background in exercise medicine or physical activity and health. All development will be completed by the end of year 1 of funding.

Screening: Phone screenings and EHR records will be used to verify eligibility status. During the phone screen participants will be asked to verify their activity status and given a short disability screener to ensure their ability to safely participate. If eligibility for cardiometabolic risk cannot be confirmed via EHR or by a physician potential participants will be able to complete screening in-person, which will involve height and weight measurement, blood pressure reading, and onsite Hba1c testing (if needed) by trained clinic staff. Less invasive screening procedures will be performed first and the in-person screening will end once eligibility is confirmed- regardless of whether all procedures were completed. Height and weight will be taken first, followed by blood pressure, and then Hba1c.

Weight: Weight will be measured twice without shoes on using a portable scale placed on a hard, flat surface. The subject will be asked to stand in the middle of the scale without touching any surface with eyes straight ahead. The subject will be asked to step down from the scale between measures. If the measures are more than 0.5 pounds apart, a third measure will be taken.

Height: Height will be measured twice without shoes. The subject will be asked to stand erect under the stadiometer with eyes straight ahead. Subjects will be asked to step down between measures. If the measures are more than one-half inch apart, a third measure will be taken.

Blood Pressure: Blood pressure will be measured with a validated automated cuff in the right arm with the patient seated comfortably with the right arm resting on a

table. Participants will be asked to rest quietly with feet flat on the floor for five minutes. The cuffed arm will be raised for 5 seconds after each inflation and a wait of 30 seconds will occur between each blood pressure reading. Blood pressure will be repeated twice with the average computed. If it is not possible to measure blood pressure in the right arm, the left arm should be utilized and noted in the patient record.

HbA1c: HbA1c will be assessed using a point of service hba1c monitor. Participants will be seated for the finger stick. Hand warmers may be used prior to the finger stick to ensure good blood flow. A sterile lancet will be used to prick the 3rd or 4th finger tip of the non-dominant hand- after the site has been prepped with a 70% isopropyl alcohol swab and is thoroughly dry. The first drop of blood will not be used, if needed the finger will be gently squeezed to obtain a second drop of free-flowing blood. A fresh finger stick will be applied and inserted into the monitor. Results will be available within 5-10 minutes.

Intervention Delivery: ActiveGOALS uses online self-directed once a week sessions with brief remote personalized e-coaching support. Social-cognitive behavior change theory and related strategies, including barrier recognition and problem-solving are included. There are 13 (20-25 minute) structured educational lessons with interactive workbook pages delivered via the GOALS online platform. After the 13 week “core intervention”, participants will continue to have access to resources on ActiveGOALSV2 for 9 more months and will receive once a month contact including a semi-personalized email from their coach and a link to online materials on a specific behavior maintenance topic (10 minutes in length). Printable workbook pages, resources, and tracking tools will also be available. The topics for the maintenance materials will be determined from output of satisfaction/ experience questionnaires administered to current ActiveGOALSV1 participants (PCOR K12 funded project) and already developed proven maintenance materials from DPP and DPP GOALS.

Brief weekly motivational feedback from a coach (with a physical activity and health or exercise science background) will be provided during the 13 week “core” intervention program via the ActiveGOALSV2 platform. Coaches will also access study administered participant PAT accounts. The coach will set goals in the PAT program to match weekly study goals and will utilize other program features (like reminders and push messaging) according to protocol developed in yr 1 of funding).

The primary behavior tracking tool will be a wrist worn PAT. However, participants will also be provided with paper and online tracking tools for physical activity to track/ report their step counts and activity minutes. I am currently working with Fitbit® monitors in other clinical patient population studies which we plan to use in this study. Currently, Fitbit devices are the most commonly used brand in the US and have been shown to validly and reliably record step counts.[69,70] As done in other studies, we will set-up PAT accounts for participants.

Outcome Assessment: All outcome measures will be collected at all time points (baseline, 6 and 12 months post-intervention) for all participants. After being consented, physical activity levels, clinical, and questionnaire measures will be

collected. Clinic visits should take 30-45 minutes to complete. Blood draws will be performed at a Quest™ lab.

Primary outcomes: Average step counts/day and time spent in moderate-vigorous (MV) physical activity will be collected from validated research grade body-worn PATs; ActiGraph wGT3X+ accelerometer (ActiGraph LLC; Pensaco-la, FL) worn on the waist during waking hours for the 7 days after a clinic visit. These accelerometers have been validated for assessing time spent in physical activity intensities and step counts in laboratory[76-81] and field settings[80,82-84] and are used to validate commercial monitors.[69,70] Data recorded in 1 second epochs will be output as activity counts [85,86] and converted to step counts and time spent in MV physical activity using accepted cut-points.[78,86]

Participants will be given a monitor and instructions (verbal, paper, and online video). Monitors will be returned by mail. Monitor on/off times will be reported via diary. To reduce reactivity, the first day of monitor data will not be used. Four or more days with at least 10 hours of wear/ day will be required for a record to be valid. Participants with incomplete data will be given the opportunity to “rewear” the monitor for a given visit (we expect <8% to require monitor rewear for any given visit; based on previous studies).

Secondary outcomes: Secondary analyses may not be fully powered (at $p<0.05$), but the findings will inform the design of an R01, fully-powered to examine the effect of ActiveGOALSV2 on cardiometabolic outcomes. Height (w/ stadiometer), weight (w/ electronic scale), waist circumference, and blood pressure (w/ automatic cuff) will be taken using validated instruments/techniques employed in previous GLB studies.

Weight: Weight will be measured twice without shoes on using a portable scale placed on a hard, flat surface. The subject will be asked to stand in the middle of the scale without touching any surface with eyes straight ahead. The subject will be asked to step down from the scale between measures. If the measures are more than 0.5 pounds apart, a third measure will be taken.

Height: Height will be measured twice without shoes. The subject will be asked to stand erect under the stadiometer with eyes straight ahead. Subjects will be asked to step down between measures. If the measures are more than one-half inch apart, a third measure will be taken.

Blood Pressure: Blood pressure will be measured with a validated automated cuff in the right arm with the patient seated comfortably with the right arm resting on a table. Participants will be asked to rest quietly with feet flat on the floor for five minutes. The cuffed arm will be raised for 5 seconds after each inflation and a wait of 30 seconds will occur between each blood pressure reading. Blood pressure will be repeated twice with the average computed. If it is not possible to measure blood pressure in the right arm, the left arm should be utilized and noted in the patient record.

Waist Circumference: The participant should be wearing loose clothing and standing

with feet together. Waist is measured using a cloth tape around the abdomen, with midpoints marked horizontally between highest point of the iliac crest and lowest part of the costal margin in the mid-axillary line. Both sides of the waist should be marked. The subject will be asked to have arms at side and to breathe in, out and hold, and then the measurement is taken. Waist measurement is recorded to the nearest quarter inch. The measure will be repeated twice. If waist measures differ by more than one-half inch, a third measurement will be recorded.

In-person clinic visits will be conducted at an on-campus clinic by trained clinic personnel, who will be blinded to randomization arm (to ensure rigor). Participants will be given instructions for the fasting blood draw (8-12 hours). Previously validated questionnaires will be administered (via computer) related to medical history/ medications, demographics/ education, healthy lifestyle habits, self-efficacy/confidence, quality of life (using PROMIS 29 and EQVAX from EQ5D), cost, patient experience; all previously used in the current K12 funded ActiveGOALSV1 study. Additional output from ActiGraph monitors (average minutes/day spent in MV physical activity, light, and sedentary) may be examined, as will data collected from PAT devices and the ActiveGOALSV2 platform. Blood samples (glucose, insulin, LDL and HDL cholesterol, triglycerides) will be drawn and processed at a Quest™ labs. Participants will be encouraged to fast for their appointment and get go to the Quest™ labs near UPITT, but can go to a Quest™ location convenient to them (25+ locations around Pittsburgh), within 10 days after the visit. To control for dietary change, participants will be asked if they attempted weight-loss through dietary change during intervention, questions on sugary beverage, water, vegetable, and protein intake will also be asked

The time commitment for accessing this version of the GOALS program will vary, but will generally not exceed 1 hour each week.

Accessing GOALS. Most participants will choose to access the GOALS website from home; others may do so from work, at a friend or family member's home, and/or from a public location, such as a library. The GOALS platform is PC- and Mac-compatible only; it does not run on any mobile devices.

Support. Coaches will be available through secure messaging within the GOALS online platform; replies are sent within two business days. Participant progress will be reviewed by the coach at least weekly. Notes will be sent to the participant either in reply to a message or in response to an issue the coach has noted (e.g. failure to log in, tracking problems, etc.). Participants who do not log in for two or more weeks will be called by telephone. If approved by the participant, PCPs are informed when their patients are enrolled. PCPs also receive 3 progress reports (4-6 weeks post-baseline, after the 6 month assessment, and after the 12 month assessment) and are contacted if questions or concerns arise that cannot be resolved by the research team.

3. * Will blood samples be obtained for research purposes?

Yes No

*** Provide the volume per withdrawal, total volume and frequency, and qualifications of individual performing the procedure:**

If needed an in-person finger stick will be obtained to determine eligibility to participate based on Hba1c and will only be done once. A 5 μ L sample of blood will be taken after finger puncture with a sterile lancet. Results will be reported in less than 10 minutes. This will be done by a trained staff person.

All venipuncture blood draws will be performed at a Quest lab by Quest staff. Quest staff are certified and experienced in drawing blood. This will be performed 3 times during the study (baseline, 6-months, and 12-months visits). Less than 15ml of blood will be drawn at each assessment.

Consent Process

Enter N/A in response to the following questions if a Waiver of Consent is requested for all research activities or if no subjects are being enrolled.

1. * Indicate where the consent process will take place and at what point

consent will be obtained:

After performing certain screening procedures, but prior to performing any of the research interventions/interactions informed consent will be obtained for the main study.

Screening consent: Screening consent will be obtained verbally over the phone or in-person for in-person screening. The PI or trained study staff will use a script to first obtain consent and then perform a short screening. If a participant must complete a second in-person screening for cardiometabolic eligibility confirmation then an addition written consent for those screening measures will be done prior to the in-person screening.

Main Study Consent: Eligible and interested participants will then be sent a copy of the study consent form to look over. The PI or study staff will then follow-up with the potential participant to see if they have questions and/or are interested in scheduling a baseline visit. In-person consent will be obtained at the baseline visit, prior to any study measures being performed. Consenting will either be done by the study PI or by trained staff using a script.

Individuals will be given the opportunity to ask questions throughout the process.

2. * Describe the steps that will be taken to minimize coercion and undue influence, including assurance that there is sufficient time for subjects to make an informed decision:

The study PI, [name] or a trained staff person will be reviewing the consent process/ form with individuals for both prior to screening and the main research study.

For screening: To avoid coercion potentially eligible participants will be given study information and will contact study staff to initiate the screening process. In the event that study staff are available in-person at GIMO for recruitment, they will not approach patients, but will be willing to discuss the study with interested participants who approach them. Participants will be informed of their rights to end the screening at any time and to refuse to answer any questions. To avoid coercion or undue influence staff will follow a script and will be trained not to deviate from the script. All staff will receive proper training and have completed relevant CITI modules before interacting with participants to reduce the possibility of coercion or undue influence.

Main study consent: To avoid coercion or undue influence eligible individuals will not be consented for the study immediately following the phone screen. Instead after

phone screening, participants will be provided with study information and the consent form by the PI or study staff. Participants will be given as much time as needed to review the consent form on their own and the PI or study staff will be available via phone or through the study email to answer questions regarding study participation. To avoid undue coercion staff will be given a guide to follow when discussing the consent with potential participants. Interested persons who indicate that they would like to sign a consent will be scheduled for an in-person visit at which the consent form will be explained to the participant by trained staff. They will be informed that attending an in-person visit does not obligate them to sign the consent form. Participants will also be informed that this study is separate from their health care and whether they choose to participate in this program or not or withdraw will not affect their relationship with their healthcare provider or with the University of Pittsburgh. They are able to login on their own anytime during open recruitment and consent to participate.

3. For studies that involve multiple visits, describe the process to ensure ongoing consent:

At subsequent visits (6 and 12-months) participants will be given the opportunity to ask questions about the consent form. The PI and study staff will also be available throughout the project via phone and email to answer questions about the study consent.

4. * Steps to be taken to ensure the subjects' understanding:

The study PI, [name] or a trained staff person will be reviewing the consent process/ form with individuals for both prior to screening (via telephone) and the main research study (in-person). Participants will be given as much time as they need to make a decision to participate. Participants will be informed of the study purpose, risks/benefits, right to withdraw and voluntary nature of participation.

5. * Are you requesting an exception to the IRB policy related to the informed consent process:

Yes No

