a. We hypothesize that participants randomized to ActiveGOALSV2 + PAT will have significantly larger (a) changes in step counts/day and % meeting moderate-vigorous physical activity goal of 150 minutes/week (to 12 months) compared to the active PAT control group. Primary outcomes will include changes in step/day and meeting the activity goal from validated research-grade PATs. Secondary outcomes will include changes in body weight, blood pressure, glycemic control, and cholesterol from study collected clinical outcomes and health questionnaires.

b. EHR data will also be used to assess program success, including program reach (comparing patients enrolling/not enrolling) and examining relationships between changes in EHR-recorded cardiometabolic outcomes and primary PA outcomes from PATs. Finally, pre-enrollment factors will be examined in relation to program success, toward better future identification of patients who may benefit from referral to programs for PA improvement. Results of this aim will be used toward developing a technology enabled referral system to an appropriate lifestyle intervention strategy with program evaluation methods that use EHR data

2. * Describe the relevant prior experience and gaps in current knowledge including preliminary data. Provide for the scientific or scholarly background for, rationale for, and significance of the research based on existing literature and how it will add to existing knowledge:

Advice from clinicians can significantly influence lifestyle behaviors. Following the American College of Sports Medicine, the American Heart Association (AHA) has recently issued a statement endorsing clinical physical activity prescription

programs. [15,18,38] In their statement the AHA outlines advantages of clinical PA advice and referral, including improved patient outcomes and lower healthcare costs.[38] Clinically administered advice on physical activity has also been shown to increase patient satisfaction with clinical care.[6,7] However, the concept of treating low physical activity levels through clinical practice is relatively new and often not part of standard care.[8-11]

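### Aim 1b (exploratory): factor analysis with invariance testing does not estimate which pre-intervention EHR factors predict activity; a regression on the outcome would

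*Protocol*

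**What the plan says.** The question is set in the protocol, Study Aims, item 1, part b: "pre-enrollment factors will be examined in relation to program success, toward better future identification of patients who may benefit from referral". Study Aims, item 2 adds that EHR characteristics predicting change in activity will be sought, as a step toward a patient phenotype for referral.

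The method is in Study Design, item 8, in the Aim 1b paragraph. Under an exploratory label it names factor analysis in Mplus, using factors taken "from participant EHR data collected prior to intervention start". The structure is to be chosen by eigenvalues, RMSEA, CFI and TLI. Then "Factor structures at the 2 time points will be compared at three levels to establish measurement invariance": configural, metric and scalar.

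The paragraph does not list the indicators, give cut-offs for the fit indices or say which two time points are meant. Study Aims, item 1 has three assessments: baseline, 6 and 12 months. The later sentence in the paragraph that carries over the Aim 1a regression approach concerns group differences in EHR-reported outcomes, not this question. The SAP has no Aim 1b text.

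**The concern.** Factor analysis answers which indicators move together. The aim asks which characteristics go with a good activity outcome. A loading, an eigenvalue or an RMSEA is not an association with steps or goal attainment, and a structure that is invariant over time is not a predictive one.

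Followed as written, the analysis would return loadings, fit indices and invariance tests, and a reader wanting to know whom to refer would have no effect estimate and no interval. The results are meant to inform a later EHR-based referral system, so this matters even for exploratory work.

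**Working it through.** **Inputs (protocol, Study Design, item 8).** Enrolment: "we plan to recruit 54 participants". Attrition: "assuming 20% attrition at 12 months", so 54 × 0.8 = 43.2, about 43 people. Test: "For a 2 sided test with alpha level set at .05". Reference mean (SD): "5250 (2200) steps/ day". Target: 2000 steps/day at 80% power. The allocation ratio is not stated; 1:1 is assumed.

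**The plan's own figure.** A two-sample t-test for 2000 steps/day with SD 2200 needs 21 per arm (power 0.82). Then 21/0.8 = 26.25, rounded up to 27 per arm, or 54 in total. The sample size is therefore reproduced for Aim 1a steps. Nothing in it was sized for Aim 1b.

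**Does invariance testing apply?** The two time points can be read in three ways.

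1. *The indicators are the pre-intervention EHR values, one per person, used at both occasions.* The two sets are then identical. With 8 indicators, the 16-variable covariance matrix has rank 8, so the joint maximum-likelihood model cannot be estimated. Separate fits would differ only through attrition.
2. *The indicators are repeated EHR records, all before the intervention.* Invariance could be fitted, but it would describe the stability of the risk-factor structure before the study and not prediction of later activity.
3. *The time points are the 6- and 12-month activity outcomes.* Equal loadings or intercepts at the two visits do not show which baseline factor predicts success. A one-factor model of the two primary outcomes alone is not identified: 2 loadings + 2 residual variances = 4 parameters, against 3 variances and covariances.

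**Could the sample carry a factor model?** These figures rest on assumed indicator numbers.

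- Suppose indicators were repeated (p per occasion, f factors, residuals correlated over time, intercepts included). The configural model has 2(p − f) + 2f(2f + 1)/2 + 2p + p + 2p parameters. For p=6, f=2: 8 + 10 + 12 + 6 + 12 = 48. For p=8, f=2: 12 + 10 + 16 + 8 + 16 = 62. The sample is 54 people at most.
- A simulation used one occasion, 8 indicators, 2 factors, loadings 0.6, factor correlation 0.3, the correct model fitted and 1000 runs. The cut-offs are conventional, since the plan gives none.

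| Result with the correct model | n=54 | n=43 |
|---|---|---|
| Eigenvalue > 1 rule picks wrong number of factors | 30% | 47% |
| RMSEA > 0.08 | 19% | 29% |
| CFI < 0.95 | 30% | 42% |

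  At n=300 each is 0.5% or less.
- The number with EHR data may be lower still, because Medical Records, item 2 allows for enrollees who are not UPMC patients.

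**What could an outcome regression show?** With z = 1.96 + 0.84 = 2.80:

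- Detectable correlation, tanh(2.80/√(n − 3)): 0.37 at n=54 and 0.42 at n=43.
- An observed r of 0.30 has a 95% interval of 0.04 to 0.53 at n=54 and 0.00 to 0.55 at n=43.
- Detectable difference for a 50:50 factor at n=43: 2.80 × 2200 × √(1/21 + 1/22) = about 1,880 steps/day.
- Detectable factor-by-group interaction, 2.80 × 2200 × √(16/n): about 3,355 steps/day at n=54 and 3,760 at n=43. Power for a 2000-step interaction is 39% and 32%.
- Baseline adjustment multiplies the detectable interaction by √(1 − ρ²). For an assumed ρ of 0.5 or 0.7 between baseline and 12 months, 3,760 becomes about 3,256 (× 0.866) or 2,685 (× 0.714).

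**The case against.** The strongest defence is that the paragraph does intend a link to outcomes. It speaks of factors related to activity and goal achievement over follow-up, and of exploring, at each time point, structures for how factors bear on activity. Mplus can fit paths from factors to outcomes. The analysis is labelled exploratory and touches no primary or secondary endpoint. All of this stands. It shows intent, but the outcome model that would carry out the intent is not written down, and what is written down is structure selection and invariance testing.

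Three stronger readings are tempting and are not supported:

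- *That Aim 1b cannot answer its question at all.* A path from factor to outcome may have been meant, and a plain outcome model on these data could detect associations of about r = 0.4.
- *That the EHR predictors are known to be measured once.* The text says only that they are collected before the intervention starts. A single occasion is an inference.
- *That the aim is to test differential benefit and wrongly leaves out treatment group.* The stated question is mainly prognostic. Patients who may benefit appear as a future use of the results, not as a hypothesis about effect modification.

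The parameter counts also say little about this plan in particular: they need an invented number of indicators and repeated measurement that the protocol does not describe. A further fair point is that regression in about 43 people is imprecise too. It is, but its imprecision is visible in an interval around the quantity that was asked for.

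**Conclusion.** The method as written does not match the question. The mismatch rests on the text alone: no outcome model is named, and invariance testing is either not estimable or beside the point under each reading of the two time points. That the sample is too small for a factor model is a supporting point, which depends on assumed indicator numbers and loadings.

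For interactions, the figure of about 3,760 steps/day is 1.9 times the 2000-step target. It assumes 43 people, 1:1 allocation, a 50:50 factor and no baseline adjustment, so it is an upper-end figure for a baseline-adjusted model under those assumptions.

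The consequence is confined to an exploratory aim and to the later referral work that would draw on it. The randomised primary comparison does not change. The text is worth changing before the Aim 1b analysis is run.

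**What to change.** Change the Aim 1b text in the protocol (Study Design, item 8), and carry it into the SAP if Aim 1b is to be covered there.

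- Remove the invariance testing and replace the factor analysis with regression of 12-month steps (linear) and 12-month goal attainment (logistic) on a short, pre-specified list of pre-intervention EHR factors.
- Adjust for the baseline outcome and randomised group. Since only 5% of controls are assumed to meet the goal at baseline, baseline moderate-vigorous minutes would serve better than baseline goal status in the goal model.
- State the time point. The same model can be repeated at 6 months if both visits were meant.
- Report each association with its 95% confidence interval, labelled hypothesis-generating.
- Add a factor-by-group term only if differential benefit is meant, and report it as an estimate with its interval rather than as a test.

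This needs no new data and only standard software. What is lost is a latent-factor summary, which a sample of 43 to 54 would support poorly.
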